10.4.5 Adherence and Retention Analyses

Data summaries will be produced (including data on subject enrollment, withdrawals, primary outcome measures, and any safety issues) on a periodic basis and reviewed by the PI, other study personnel and the independent safety monitor.

10.4.6 Baseline Descriptive Statistics

Baseline data will be summarized using descriptive statistics, as appropriate.

10.4.7 Planned Interim Analyses

10.4.7.1 Safety Review

The data summaries will be reviewed by an internal committee comprising the PI and members of the research team to monitor data quality, study progress and determine whether the study should change in any way or be stopped. Data summaries will be sent to the independent safety monitor on a quarterly basis for a safety review (at the monitor's discretion) and to determine whether the study should change in any way or be stopped. Serious (expected or unexpected) adverse events will be reported immediately to the PI (by a subject or member of the research team).

Minor adverse events (e.g. mild discomfort of the lids) will be recorded on a subject's data sheet at the time of occurrence; they will subsequently be reported internally for that study. Minor adverse events will also be reported on an annual basis to the relevant IRB committees, as part of the annual IRB review of each approved study.

10.4.7.2 Efficacy Review

Preliminary data analyses will occur periodically.

10.4.8 Additional Sub-Group Analyses

Subgroup analysis is not part of the analysis plan

10.4.9 Multiple Comparison/Multiplicity

P-values used to indicate significance will be corrected where appropriate. There is no plan for multiple comparisons.

10.4.10 Tabulation of Individual Response Data

Individual response data will be recorded on data sheets and input into Excel spreadsheets.

10.4.11 Exploratory Analyses

No exploratory analyses are planned.

10.5 Sample Size

Sample size was estimated based on available preliminary data at the time of study planning, estimating 40 would need to complete the crossover with an estimated attrition of 10 giving a total of 50 planned for enrollment. However, this was able to be greatly reduced given the size of the effects measured in the interim analyses conducted after 8 participants had completed the crossover. The final sample size required to measure the primary outcome with power of 0.80 and type II error of alpha 0.05 was 16.

10.6 Measures to Minimize Bias

10.6.1 Masking AND RANDOMIZATION Procedures

Masking:

Subjects will be masked as to which of the two devices is the new treatment. They will simply be told that they are evaluating two non-surgical treatments for blepharoptosis. A debriefing questionnaire will be administered after the second period of the crossover to determine whether subjects guessed that the MLP was the new treatment and the KTFS was the comparison treatment.

Data assessors (e.g. Turkers) for the primary outcome will be masked since they will not be familiar with the study or the 2 treatments. They will review videos of blink dynamics which have been cropped to show only the eye region so the subject cannot be identified (see Measurements of Eye Lid Kinematics in section 10.4.1).

The person conducting statistical analyses of the primary outcome will be masked.

It is not possible to mask the study team member who will fit and provide training for the MLP device, since the fitting requires specialist expertise. That study team member will avoid telling subjects that the MLP is the new treatment. Furthermore the quantification and analysis of the primary outcome will be conducted by masked data assessors.

A person external to the study team will fit and provide training for the KTFS. Again, it will not be possible to mask this person. However, this person is highly experienced in using Kinesio Tape, a proponent for its use for blepharoptosis, and has received training in fitting Kinesio Tape for ptosis. Again they will avoid telling subjects that the KTFS is the comparison treatment, and the quantification and analysis of the primary outcome will be conducted by masked data assessors.

Recruitment for the clinical trial has been very successful so far. However the greater number of subjects than initially anticipated means that we have been running into problems when trying to schedule visits with the Physical Therapy Team Member (PT) for fitting of the kinesiotape frontalis sling (KTFS). The PT sometimes does not have sufficient room in her clinic schedule to accommodate a taping visit per the schedule in the protocol. We've described a backup plan below to ensure that participants receive taping visits per the original protocol schedule even when the PT is not available. Please note that the proposed plan requires that the PT will provide oversight of all taping visits by reviewing videos of the taping sessions.

As a backup plan in case scheduling constraints mean that it is not possible to schedule a taping visit with the PT:

1. The PI will perform the tape placement.
2. The PI or the research staff will be in attendance as the participants practice placing the tape.
3. The entire process will be recorded and the video loaded onto a secure server or shared via Institutional DropBox
4. The PT will be responsible for reviewing the videos within two days of placement, to ensure proper technique.

Randomization

Participants will be assigned to one of two possible treatment allocations: 1) MLP then KTFS or 2) KTFS then MLP. The allocation will be performed using software that implements the process of minimization. The first participant will be assigned randomly with each subsequent participant assigned in such a way as to approximately balance the number of participants who are 65 years of age and over and who have acute vs chronic ptosis. We propose to balance for these two factors because adults over the age of 65 typically have thinner and looser eyelid skin, and participants with acute ptosis may recover while enrolled in the study, which may affect outcomes. Letter codes, randomly assigned to each of the treatment allocations by a researcher external to the study will be used by the software. The code breaker will be kept in a sealed envelope in a location known only to the external researcher. Data provided to the masked data assessors and the masked person conducting statistical analyses will use the letter codes to identify treatment allocation.

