10.2 Statistical Hypotheses

Primary outcome measure:

Statistics for the participant characteristics will be presented in terms of mean \pm standard deviation or median \pm interquartile range (25th to 75th). Within subjects repeated measurements, linear mixed effects regression will be used to determine the effect of treatment condition on the IPF values (spontaneous and resting state open), with a random intercept for the subject factor. Subject age, gender, blink sequence (the order of the blink recorded in the video), and the order of interventions (whether evaluated in the first or the second arm of the crossover) will be covariates of interest. Effect of each covariate will be investigated alone, and only statistically significant ($P < .05$) covariates will be included in the final regression model, from which, the estimated marginal means and their 95% confidence interval (CIs) will be reported for each of the outcomes. Missing values at the T2 time point will be imputed from another time point within the same subject (T1 by default or T0 if both T1 and T2 were not available). For volitional blinks, a test of proportionality will be performed to determine the effect of the 3 treatments on the probability of eye not fully closing.

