10.4 Description of Statistical Methods

10.4.1 General Approach

This clinical trial uses a prospective, double-masked, within-subjects crossover design. Descriptive statistics for continuous data for each of the primary and secondary endpoints will be presented as means with standard deviations or medians and ranges, as appropriate. The normality of the data will be examined and appropriate statistics and descriptives used based on the results.

Measurements of Eye Lid Kinematics:

Our main measures of device efficacy involves the measurement of eyelid kinematics from video recordings made at various timepoints throughout the clinical trial. **Measurements may be made manually within NIH's image J software, automatically using a software we create (in Python or similar platform), or using crowdsourcing with Amazon Mechanical Turk.**

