10.4.2 Analysis of the Primary Efficacy Endpoint(s)

We will use a repeated measures mixed effects model for analysis of the primary outcome measure (change in interpalpebral fissure during opening and spontaneous blinking). The model will include a random subject-level intercept and a fixed treatment effect (MLP or KTFS). A repeated measures model will be used with primary timepoint for analysis being after 1 week of use. . The model will also include fixed effects of treatment order (i.e., MLP: KTFS vs KTFS:MLP), and crossover period (period 1 or 2), and will control for age and sham opening interpalpebral fissure.

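### Acute v chronic ptosis is a minimisation factor because acute cases may recover, but the primary model has no acute-by-period term to absorb recovery between periods

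*Combined protocol and SAP*

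**What the plan says.** Section 10.6.1 allocates treatment order by minimisation, so as to "approximately balance the number of participants who are 65 years of age and over and who have acute vs chronic ptosis". The reason given for the second factor is that "participants with acute ptosis may recover while enrolled in the study, which may affect outcomes".

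The primary model is described twice. Section 10.4.2 has a random subject intercept, treatment, treatment order, "crossover period (period 1 or 2), and will control for age and sham opening interpalpebral fissure". Section 10.2 lists as candidate covariates "Subject age, gender, blink sequence (the order of the blink recorded in the video), and the order of interventions", and adds a screen: "Effect of each covariate will be investigated alone, and only statistically significant" ones (P<.05) enter the final model. Age, the other minimisation factor, appears in both descriptions. Acute/chronic status appears in neither, whether as a main effect or in interaction with period.

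**The concern.** The plan itself names recovery of acute cases as a source of outcome variation, balances allocation for it, and then gives the model no means of accounting for it.

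A crossover does not remove this automatically. Status at enrolment is constant within a person and cancels from the MLP-KTFS contrast. Recovery is a change over time in one subgroup. Under Sections 7.3.2 and 7.3.7 the two end-of-week assessments (Visits 3 and 6) are about 5 weeks apart: 2 weeks of washout plus a second period of 3 weeks. The period effect in Section 10.4.2 is common to all subjects, so it takes out the mean recovery and leaves acute subjects above it and chronic subjects below it.

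The sham covariate does not clearly help. Section 7.3.2 says that a sham can be recorded for the MLP only, so it does not supply a reading in each period.

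Two things are at stake: precision of the device contrast, and a shift in its estimate if acute subjects are unevenly split between the sequences.

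**Working it through.** **The plan's figure.** Section 10.5 gives N=16 for power 0.80 and 0.05, with no difference, SD or sidedness, so it cannot be reproduced. Working backwards at two-sided 0.05, the standardised within-person difference is (1.960+0.842)/√16 = 0.700 by the normal approximation, or 0.753 with the t distribution on 14 df for a two-sequence crossover. If the difference is the 1 mm of Section 4.2.1 (an assumption), the SD of the within-person difference is 1/0.753 = 1.327 mm. The true SE of the device estimate is then 1.327/√16 = 0.332 mm.

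**Other inputs.** The documents do not give the acute share p or the extra recovery r of acute subjects between periods. Both are varied below.

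**Main effect.** In simulated crossovers fitted with a random intercept, adding acute/chronic as a main effect left the device estimate identical. The mean SE was 0.3258 with and without it when nobody recovers, and 0.4198 v 0.4197 with 2 mm recovery and half the subjects acute. A main effect alone gains nothing.

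**Variance.** Without an acute-by-period term, the variance of the within-person difference rises from 1.327² to 1.327² + p(1-p)r². For p=0.5 and r=2 the addition is 0.25×4 = 1.00, so 1.762 becomes 2.762. For p=0.25 and r=1 it is 0.1875×1 = 0.19.

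**Power.** There were 40,000 simulated trials per setting, with one value per person per period, 8 subjects per sequence, acute status balanced by sequence and a true difference of 1 mm:

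| Acute share | Recovery (mm) | Mean model SE without term | Power without | Type I error without | Power with acute-by-period |
|---|---|---|---|---|---|
| 25% | 0 | 0.326 | 0.799 | 0.048 | 0.793 |
| 25% | 0.5 | 0.331 | 0.792 | 0.049 | 0.796 |
| 25% | 1 | 0.345 | 0.765 | 0.040 | 0.795 |
| 25% | 2 | 0.399 | 0.651 | 0.020 | 0.794 |
| 50% | 0 | 0.326 | 0.801 | 0.050 | 0.796 |
| 50% | 0.5 | 0.333 | 0.789 | 0.047 | 0.797 |
| 50% | 1 | 0.352 | 0.753 | 0.036 | 0.796 |
| 50% | 2 | 0.420 | 0.605 | 0.014 | 0.796 |

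The actual spread of the estimate stayed at 0.331-0.333 throughout. Under exact balance, therefore, the estimate is unaffected; the model only reports it as less precise than it is.

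**Imbalance.** The device estimate is half the difference between sequences in the mean period change, so recovery shifts it by r × (p₁ - p₂)/2, where p₁ and p₂ are the acute shares in the two sequences. With 4 of 8 v 2 of 8 acute and r = 2 mm, the shift is 2 × (0.50 - 0.25)/2 = 0.25 mm. With 4 v 3 it is 2 × 0.125/2 = 0.125 mm. The interaction removes both.

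**The case against.** **Definition of change.** The endpoint is a change in fissure. Section 7.3.2 takes device-free measures during training, and Section 7.3.7 schedules recordings at Visits 1 and 4. If change is taken from each period's own device-free baseline, recovery before that baseline is at least partly subtracted out. This stands. The plan does not define the reference, so the losses above are those with no such correction.

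**Level of data.** Section 10.2 treats the order of blinks as a covariate, which suggests analysis of individual blinks with only a random subject intercept. The direction then reverses. Take 16 subjects, 6 acute, 2 mm recovery, an SD of 1.33 mm and, by assumption, 5 blinks per period with SD 0.6 mm. The pooled residual variance is [2.5×(14×1.769 + 16×0.9375) + 128×0.36]/142 = 1.025, and the SE is √(2×1.025/80) = 0.160. Simulation gave 0.159, against a true spread of 0.327 and type I error of 0.36. Adding acute-by-period does not cure this: (2.5×13×1.769 + 46.1)/141 = 0.735, an SE of 0.136. The interaction helps only once the within-period clustering is handled, so this also stands and shapes the fix.

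**Stronger readings.** A reader might infer that the trial is under-powered against its stated 0.80. The documents do not support that. Section 10.5 bases N=16 on effects seen in 8 completers; if the variability came from the same data, it may already contain recovery noise. A reader might also infer that omitting the factor itself widens the interval (the main effect has no influence), that age should be recoded at 65 to match allocation (also constant within a person, so it should do nothing for the contrast), or that the factor was deliberately judged unnecessary (no reason is given).

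**Few acute subjects.** The interaction could be poorly estimated. In the 4 v 2 split, the squared correlation of acute status with sequence is 0.125²/(0.375×0.625) = 0.067, so the SE rises by a factor of √(1/0.933) = 1.035. That is modest beside a possible 0.25 mm shift.

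**Conclusion.** The point holds, conditionally. The missing element is the acute-by-period interaction, and it matters only if acute subjects improve materially between periods.

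With one value per person per period and 25-50% acute, power drops by about 1 point at 0.5 mm recovery, to about 0.75-0.77 at 1 mm and to about 0.61-0.65 at 2 mm. These figures start from an assumed 80% power for 1 mm when nobody recovers. Under exact balance the error is conservative: the risk is a missed effect, not a false positive. Under approximate balance the estimate can also move, by 0.25 mm in the 4 v 2 example, a quarter of the 1 mm in the endpoint.

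The acute share, the recovery size and the use of 1 mm as the design difference are assumptions, so no shortfall against the stated 0.80 can be derived. This is a cheap improvement to the plan, not a flaw that invalidates it.

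**What to change.** In Section 10.4.2, prespecify acute/chronic ptosis and its interaction with period as fixed effects. State that they stay in the model whatever the P<.05 screen in Section 10.2 shows. Run the analysis on one value per subject per period or, if individual blinks are modelled, add a subject-by-period random effect. State in the same place whether change is measured from each period's own device-free baseline.

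The cost is SAP wording only, because the factor is already recorded for allocation. The interaction uses one degree of freedom of the within-person comparison. If nobody recovers and the sequences are balanced, power goes from 0.80 to about 0.795, a loss of 0.01 or less; with an uneven acute split the cost is somewhat higher (SE about 3.5% wider at 4 v 2).

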10.6.3 Breaking the Study Blind/Participant Code

The PI will determine if for safety reasons, the study staff needs to be unblinded on a subject by subject basis and/or during a specific study visit

11 SOURCE DOCUMENTS AND ACCESS TO SOURCE DATA/DOCUMENTS

Data collection sheets will be completed for each subject enrolled into the clinical study. Data Collection sheets will be study visit specific and the research technician (oversight by PI) will review and sign each subject visit for completeness and document any minor protocol deviations. Investigator's signature or record locking serving as attestation of the responsibility for ensuring that all clinical data entered on the data collection sheets are complete, accurate and authentic.

All computer generated data will be stored on internal MEEI servers located on encrypted, password protected MEEI computers. Only the PI and researchers specific to this study who have been granted access to the data by the PI will be able to view the data in the MEEI network protected folder. If data is sent out to be analyzed the data will be de-identified. The data will contain subject identification numbers, which are linked to identifiers on a separately secured spreadsheet. The data will be coded by assigning each participant a subject identification number and removing any identifiable information. The code will be secured by the PI and Study staff in the drive located on encrypted, password protected computers at Schepens. The code that links information that can identify the participant to the data collected for this research will be kept separate from their health information, which will be destroyed once this study is complete and the manuscript has been published.

12 QUALITY ASSURANCE AND QUALITY CONTROL

The Principal Investigator will be responsible for quality assurance during this study. The Principal Investigator will confirm that the study device is stored correctly. The Principal Investigator will also

Clinical Trial to improve the magnetic levator prosthesis (MLP) including the development and testing of a novel adjustable force system and comparison to the Kinesio Tape frontalis sling (KTFS) Version 1

train study staff on the protocol procedures and will confirm staff can confidently complete the study related assessments.

13 ETHICS/PROTECTION OF HUMAN SUBJECTS

13.1 Ethical Standard

All staff designated to work on this trial will have CITI certification for confirmation of GCP training and their CV's, licenses and other forms of certifications related to conducting research will be kept with the study regulatory binder.

13.2 Institutional Review Board

The IRB of record for this study will be the Mass General Brigham IRB. The protocol will be approved prior to subject enrollment and will be reviewed yearly after initial approval. Any adverse events or serious adverse events will be reported to the Mass General Brigham IRB office; however this is not expected to occur because this is a minimal risk protocol.

13.3 Informed Consent Process

Subjects are required to sign an informed consent before participating in the study. The consent will be signed in front of a study team member (witness). The witness and investigator will sign and date the consent form. A note will be made on the study record that the informed consent was signed by the participant. The informed consent will follow the guidelines set by the Mass General Brigham IRB. A copy of the consent form will be given to the participant. A member of the study team will review the study procedures, visit schedule, risk and benefits, alternative treatments and rights to withdraw and ask questions with all potential subjects before signing the consent. Every participant has a right to withdraw at any time from the study without affecting their care or relationship with the treating physician and participating institution. The financial responsibilities of the participant will be discussed. All participants are required to sign a Health Insurance Portability and Accountability Act (HIPAA) form before participating (unless this is combined with the consent). A study member will explain and discuss with the participant their confidentiality rights as described in the HIPAA form.

13.3.1 Consent/assent and Other Informational Documents Provided to Participants

Consent and assent forms have been uploaded.

13.3.2 Consent Procedures and Documentation

Participants who are determined by their clinical specialist to have Blepharoptosis will receive a recruitment packet from the services' administrative assistant. If subjects are identified by a pre-screening (i.e. chart is prescreened and tagged by the clinical research office) and they are interested in the study they will schedule another appointment in the Vision Rehab Service research lab at Massachusetts Eye and Ear Infirmary, [name]. The scheduler/study coordinator/research assistant will inquire about any prior diagnosis of dementia or significant cognitive impairment, and if so coordinate the primary caregiver to also attend the visit.

Pre-Screening and assent for decisionally impaired: Approved study staff will administer a short cognitive pre-screening (mini-mental state exam, MMSE) to determine if there is any cognitive impairment. The MMSE will not be linked to a study identifier and will be retained for aggregate

analysis only. If score is <18, the individual is not eligible. If score is 18-23 (may be decisionally impaired), an assent process will occur, and consent obtained from the primary caregiver (the health care proxy (if one has been named), or the spouse or family member (in that order of preference)).

Children: If the study candidate is a child, one parent will sign the consent and children under 14 will sign the assent and children over 14 and older will sign the consent (unless decisionally impaired as determined with the same MMSE criteria).

Consent procedures: The PI has approximately 10 years experience in providing informed consent to patients with neurological disorders, and >15 years providing eye care for this population. One of the trained clinical research technicians will perform the informed consent in a private room at Massachusetts Eye and Ear. The PI will not be directly involved in the consent process and he will not be in the room during signature, to prevent any sense of pressure/coercion. Alternatively, informed consent may be performed over the telephone, to limit the face to face time so long as the COVID-19 pandemic is a concern. The study will be explained to the potential participant and they will be asked to read (or have read to them) and sign the approved informed consent (or assent) form before participation in the study. Alternatives to participating will be explained. They will be given ample opportunity to discuss all aspects of the study before signing the form. A detailed explanation of the interventions and how they work will be given, including showing them the devices (pictures of the devices if consented on the phone) and allowing them to ask questions. The study staff will leave the room allowing the prospective participant and any family members to discuss in private. Prospective participants will be specifically offered the opportunity to discuss the interventions and the study with the PI, their ophthalmologist, and family members/caregivers prior to consenting. A copy of the consent form will be given to the participant.

